03/04/2018

IRB #17-0815-F2L

University of Kentucky College of Dentistry Division of Periodontology

Ridge Preservation with Leukocyte Platelet Rich Fibrin: A Clinical, Radiographic, and Histomorphometric Study

[name] [name]

Committee Chair

[name]

Committee Advisors

[name]

[name]

Background and significance:

After a tooth extraction, the alveolar process loses a mean of 3.8 mm horizontally and 1.2 to 1.6 mm vertically, mostly within the first 3 months of healing. ^{1, 2} It loses up to 50% of its original dimension during the first year. ³ This dramatic ridge resorption compromises prostheticallydriven implant placement. Resorption is more pronounced in the mandible than in the maxilla, and usually the buccal side loses more volume than the lingual.^{4, 5} Alveolar ridge preservation has been used effectively to limit ridge reduction post tooth extraction.⁶⁻⁹ Current methods in socket grafting or ridge preservation include the use of autogenous grafts (graft from the same individual), allografts (graft from different individual of the same species), xenografts (graft from different species), and alloplasts (synthetic graft materials). These methods include naturally derived or synthetic, resorbable or non-resorbable membranes. ¹⁰⁻¹² To date, the literature does not present clear guidelines for the type of bone graft material, membrane, or surgical procedure for ridge preservation.¹³

The use of the membrane prevents invagination of the epithelium, and gives the osteoblasts time and space to form new bone.^{4, 14} The ideal membrane should be biocompatible, malleable, and able to exclude the soft tissue.^{15, 16} In clinical studies, different types of barrier membranes have been used, with different rates of bone formation.^{4, 5} Usually, resorbable and permeable synthetic membranes require tension free primary closure, which increases surgical complexity, reduces the amount of keratinized gingiva, disrupts the architecture of soft tissues, and compromises the vascularity of the flap with periosteal releasing incisions. The micro-porosity of high-density polytetrafluoroethylene (dPTFE) can exclude the bacteria and protect the graft even when exposed to the oral cavity.¹⁷ The successful use of (dPTFE) membrane has been demonstrated in animal and clinical trials.¹⁸⁻²⁰ Also, dPTFE membrane can be used predictably without a bone graft material to preserve the extraction sites.²¹

In a recent animal study, using autogenous bone particles does not have a significant effect in preventing ridge resorption²² while, xenografts maintain the dimensions of the ridge better compared to allografts alloplastic materials and natural healing. Sockets grafted with alloplastic materials (after >12 weeks) provide the highest amount of vital bone (45.5%), and the least amount of remnant graft material (13.7%), and connective tissue (38.4%), while, allograft

provided (30%, 21.7%, 51%), and xenograft provided (35.7%, 19.3%, 44.4%) respectively.²³ Some literature suggest that implant primary stability could be affected by the bone graft material remnants.²⁴

There is limited evidence to support the use of growth factors, human platelet-derived materials, platelet-rich fibrin, and stem cells as adjuncts to ridge preservation.²³ Leucocyte and platelet-rich fibrin (L-PRF) alone or in combination with a graft material can improve soft tissue healing, bone regeneration, ridge preservation, and reduces infection rate,²⁵⁻³⁰ L-PRF was introduced by Choukroun in 2001. L-PRF is composed of a dense high cross-linked fibrin mesh with the entrapped leucocytes and platelets, which in turn releases growth factors and cytokines for 7 days.^{31, 32} Some investigators have reported a positive effect on bone regeneration^{33, 34} while others failed to find any effect.³⁵ L-PRF outcomes for ridge preservation are comparable to those obtained with xenografts or allografts bone graft particulates, however, it is superior to alloplasts materials and natural healing. Use of L-PRF also provides additional advantages such as stimulating natural healing with patients own growth factors without any remnants and at a low cost.³⁶

The purpose of this clinical randomized study is to investigate the effect of L-PRF plug on the quality of newly formed bone in the preserved socket using non-resorbable membrane (d-PTFE).

Null hypothesis:

The use of L-PRF plug, in combination with non-resorbable, open barrier membrane technique to fill the extraction sockets will have no effect on the quality of the newly formed bone nor on the dimensional changes of the ridge, compared to non-resorbable, open barrier membrane technique with natural blood clot.

Alternative hypothesis:

The use of L-PRF plug, in combination with non-resorbable, open barrier membrane technique to fill the extraction sockets will have a positive effect on the quality of the newly formed bone and on preserving the dimensions of the alveolar ridge, compared to non-resorbable, open barrier membrane technique with natural blood clot.

Specific aims:

The primary aim is to assess the quality of the newly formed bone at the time of implant placement by comparing the percentage of new vital bone in the histomorphometric analysis. The second aim is to assess the primary stability of the implant using the resonance frequency analysis (RFA) and insertional torque (IT) of the implant. The third aim is to assess the horizontal and vertical changes of the residual bony ridge using Cone Bean Computerized Tomography (CBCT) analysis at baseline immediately after tooth extraction and prior to implant placement at 12 weeks of healing. The fourth aim is to assess the soft tissue healing with a series of intraoral occlusal photographs.

Material and methods

Study Population

Forty-eight subjects will be recruited from the patient population of the University of Kentucky College of Dentistry clinics and will be randomly assigned into a control group and a test group by computer-generated randomization table. Following informed research consent, all subjects will a complete health history questionnaire. Twenty extraction socket sites of the test group will be filled with autogenous L-PRF Plug (Intralock®) and d-PTFE membrane (Cytoplast®) will be laid on the top to seal the extraction socket. In the control group, d-PTFE membrane (Cytoplast®) will be laid on the top of twenty extraction sockets to allow natural blood clot formation in the extraction socket. To account for expected attrition, an additional four patients will be tried to be recruited in each group.

Inclusion and exclusion criteria:

The subject must have an unsalvageable tooth that is planned for extraction and delayed implant placement. The tooth should be free of acute odontogenic infections, and only the extraction sockets with minimal to moderate bony defect will be included in the study.

Any patient who is planned for full mouth extraction, who is a heavy smoker (more than 10 cigarettes a day), who has a history of malignancy, chemotherapy, radiation therapy, immunosuppressive disease, uncontrolled systemic disease, or any contraindications to surgical procedures will be excluded from the study. Females who are pregnant or breastfeeding will be excluded as well. Also, for multi-rooted teeth, if the most coronal part of the interradicular septum is less than 5 mm below the crest of the bone, tooth will be excluded from the study.

Subject visits:

Screening Visit: All subjects will receive a comprehensive oral and periodontal examination. Patients who fulfill the inclusion criteria will continue in the study and will complete the baseline visit and all subsequent visits. After providing a thorough explanation about the study, an informed research consent will be obtained. The clinical examinations will be done on all patients by the same investigator throughout the study. If the patient is eligible, a pre-operative assessment and treatment planning will be done at this stage.

Visit 1 (Baseline): Tooth extraction, ridge preservation procedure, and CBCT will be performed. Autologous blood will be withdrawn and centrifuged to make the L-PRF plug in the test group. Intraoral occlusal photograph will be taken before and after tooth extraction.

Visit 2 (1-week from the baseline visit): Suture removal, and post-surgical follow-up evaluation will be performed and intraoral occlusal photograph will be taken.

Visit 3 (4-week from the baseline visit): Non-resorbable membrane will be removed and intraoral occlusal photograph will be taken.

Visit 4 (12-week from the baseline visit): A conventional or digital impression of the site will be taken and intraoral occlusal photograph will be taken. Then CBCT will be performed for implant planning.

Visit 5 (14-week from the baseline visit): A bone core biopsy will be performed and will be followed by the implant placement along with the primary stability assessment. Intraoral occlusal photographs will be taken before and after the surgery.

Table (1). Data collection for each visit of the study is described. All procedures described above are Standard of Care except bone core biopsy in visit 5 is a research components.

Intraoral occlusal photograph:

Intraoral photograph will be taken to evaluate soft tissue healing. Standardization of photographs will be tried by using an occlusal mirror with a 40° angle to the occlusal plane of a patient in a supine position. Fixed camera settings will be used in all sessions. Photos will be taken at the base line, 1-week, 4-week, 12-week and 14-week visits.

L-PRF plug preparation Protocol:³⁷

A venipuncture with a 21 Gauge butterfly needle will be used to collect up to six 9 ml tubes of blood. Tubes immediately are placed into the IntraSpinTM centrifuge. and counterbalanced with each other. Centrifugation will be run at 2700 rpm for 12 minutes, however, in patient taking anticoagulant medication up to 18 minutes are recommended. The centrifugation would separate the red blood cells layer at the bottom, the platelet poor plasma layer on the top, and the L-PRF fibrin clot in the middle of the tubes. Fibrin clots will be taken out of the tubes and then will be placed in the small white cylinder of the XpressionTM box, and compressed until holder is level to cylinder. The plugs stay viable up to 3 hours, if they are re-hydrated with the PRF exudate.

Ridge preservation surgical Procedure:

After administration of the local anesthetic (LA), full thickness buccal and lingual flaps will be elevated about 3-4 mm pass the socket bone crest. Atraumatic tooth extraction will be performed using peizosurgery, periotomes and/or elevators with root sectioning on multi-rooted teeth. The socket will be curreted, then copious saline irrigation will be applied. The extraction sockets of the test group will be filled up to the crest of the ridge with 3-5 L-PRF Plugs, depending on the size of the socket, and condensed with the amalgam condensor. A d-PTFE membrane (Cytoplast®) will be laid on the top of the extraction socket of test and control group and will be inserted 3-4 mm beyond the bone crest. Flap will be re-positioned to its original position with no attempt to get primary closure for either group.

Implant digital surgical guide

A digital or conventional impression of the site will be taken to obtain an STL file, and a DICOM file from the CBCT at 12-week visit. Then surgical guide will be fabricated (Dreve®) utilizing the coDiagnostiXTM software in order to plan for the future implant size and location in a prosthetic driven manner. The same guide will be used for the bone core sample, with a trephine bur of a suitable size.

Implant placement surgical Procedure:

Using the implant surgical guide a core bone biopsy will be taken from the healed extraction site. Then the implant will be placed as recommended by the manufacturer (BLT, Straumann®), and additional bone grafting will be done if needed. The implant stability quotient (ISQ), and insertional torque (IT) will be recorded at the implant placement time to assess the primary stability.

Pre- and Post- operative instructions:

Prophylaxis Antibiotics: Standard of care Amoxicillin 2 g will be given one hour prior to surgery or Clindamycin 600 mg one hour prior to surgery if the subject is reported to be allergic to Penicillin.

Analgesic: NSAID will be prescribed as needed. Patient will be instructed to use Chlorhexidine 0.12% mouth rinse twice a day for five weeks. The patient will be instructed to be refrained from brushing or flossing to the surgical site for 10 days.

Histomorphometric assessment:

The core bone biopsy will be harvested using the surgical implant guide at the time of implant placement. It will be placed in a container with 10% neutral buffered formalin. The sample will be sent for light microscopy histologic slides preparation in the lab. The bone specimens will be demineralized in EDTA for a month and embedded in paraffin wax. Bone sections (~5µm) will be obtained using the Leica (RM 2255, Leica, IL) microtome. For each biopsy specimen, longitudinal section will be used for light microscopic examination. Histomorphometric analysis will be performed on three fields for each section using specialized software (Bioquant, Nashville, TN). Percentages of newly formed bone, residual connective tissue, and any material remnants will be measured based on the averages of the percentages at a magnification of 100X.

CBCT acquisition:

CBCT images^{38, 39} will be acquired by i-CAT FLX Cone Beam 3D system (Imaging Sciences, Hatfield, PA, USA) at baseline immediately after tooth extraction, and prior to implant placement at 12 weeks post extraction. Scans will be obtained at the Standard protocol (360° rotation, 300 frames, 120 kVp, 5 mA, 3.7 sec, 16 x 8 cm FOV, 400 µm voxel size).

CBCT analysis²⁶

The analysis of the CBCTs will be performed according to the analysis described by Jung et al. (2013). To perform the CBCT measurements, scans taken immediately after extraction (CBCT 0), will be superimposed on scans taken at 12 weeks post extraction (CBCT 12) using InVivo 5.2 imaging software (Anatomage, San Jose, CA, USA). For the superimposition of the cross-sectional slices, the fixed anatomical landmarks include the palatal vault in the maxilla, the lower border and angle in the mandible, where no changes would occur after extraction. Both data sets would be spatially aligned in order to obtain a match. To set a reference, in single-rooted teeth, the most apical point (A) of the extraction socket is defined in the baseline image (CBCT 0), while in the multi-rooted teeth point (A) to be the most coronal point on the interradicular septum, right at the center of the extraction socket (Fig 1). Two reference lines are subsequently drawn. The vertical reference line is drawn in the center of the extraction socket crossing (A) reference point. The horizontal reference line is drawn perpendicular to the vertical line crossing the apical reference point (Fig 2).

The following measurements are then performed (Fig. 3):

- 1. The thickness of the buccal plate (BP) on CBCT0 will be measured at 1, 3 & 5 mm below the lingual bone crest.
- 2. Horizontal ridge width (RW) will be measured at 3 levels: 1,3,5 mm below the buccal bone crest.
- 3. Vertical resorption of both the buccal and lingual plates will be measured in millimeter.
- 4. Socket fill percentage will be assessed based on the highest point of viewable mineralized bone on CBCT12.

Primary outcome variable is socket fill with new bone. Secondary outcome variables are changes in horizontal width at crest -1mm, 3 mm, and 5 mm levels; and vertical resorption at the lingual and buccal side.

Figure 1. In single-rooted teeth the most apical point (A) of the extraction socket is defined in the baseline image (CBCT 0), while in the multi-rooted teeth point (A) to be the most coronal point on the septum, right at the center of the extraction socket.

Figure 2. Two reference lines are subsequently drawn. The vertical reference line (the blue interrupted line) is drawn in the center of the extraction socket crossing the apical reference point. The horizontal reference line (the red interrupted line) is drawn perpendicular to the vertical line crossing the apical reference point.

Figure 3. Following measurements are then performed:

- 1. The thickness of the buccal bone plate is to be measured at 1, 3 & 5 mm below the lingual bone crest (PB Width), on baseline image only.
- 2. Horizontal ridge width at 3 levels (crest -1 mm (RW-1 mm), crest -3 mm (RW-3 mm) & crest -5 mm (RW-5 mm)) below the most coronal point of the buccal crest, in millimeter.
- 3. Vertical resorption on both the buccal and palatal side, in millimeter.
- Socket fill as being the highest point of viewable mineralized bone. Percentages of socket fill will be measured by comparing the initial depth of the socket and the depth after 12 weeks of healing.

Adverse Effects:

If patients experience pain that cannot be managed by the prescribed analgesic, they will be told to contact the principal investigator for follow-up.

The membrane will be left on the extraction socket for 4 weeks, if there is no sign of infection, otherwise any infection will be treated which may necessitate the removal of membrane.

Subjects will be monitored for other adverse reactions throughout the study. All adverse events will be managed and documented by the principal investigator.

Statistical Analysis:

For the expected result, A sample size of 20 in each group will have at least 80% power to detect an effect size (ES) of 0.9 using a two groups t-test with a 0.050 two-sided significance level. The t-test will be used for the histomorphometric analysis, ISQ and, insertional torque. While, Manova will be used for the CBCT multiple measurements. Subject incentives will consist of 50\$ Gift card, and a free follow up CBCT after completion of visit 5.

References:

- 2. Van der Weijden F, Dell'Acqua F, Slot DE. Alveolar bone dimensional changes of post-extraction sockets in humans: a systematic review. *J Clin Periodontol* 2009;36:1048-1058.

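### Socket fill, named the primary outcome variable among the CBCT measures, has no prespecified baseline covariate; adjusting for initial socket depth and root type may improve precision, by an amount the documents do not allow one to fix

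*Protocol*

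**What the plan says.** The protocol's CBCT analysis section states: "Primary outcome variable is socket fill with new bone". The Figure 3 legend gives the measurement: "Percentages of socket fill will be measured by comparing the initial depth of the socket and the depth after 12 weeks of healing". The exact formula is not written out. Depth refers to point A, which is the socket apex in single-rooted teeth and the top of the septum between the roots in multi-rooted teeth. Multi-rooted teeth are excluded when that septum lies less than 5 mm below the crest.

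The Statistical Analysis section gives one method for these data: "While, Manova will be used for the CBCT multiple measurements". It names no covariate. Subjects are "randomly assigned into a control group and a test group by computer-generated randomization table", and no stratification by depth or root type is stated.

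The SAP output shows unadjusted Welch t-tests with 11 per arm for variables labelled percent, RW changes and RH changes. It then regresses RW and RH on buccal plate width, separately within each arm. No table is labelled socket fill and none uses socket depth.

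A separate conflict affects how much weight this point carries. The Specific aims section makes the primary aim bone quality, assessed by "comparing the percentage of new vital bone in the histomorphometric analysis".

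**The concern.** Forming a percentage of baseline looks like baseline adjustment, but it is adjustment only under proportionality. Take 2 mm unfilled as an illustration: fill is 60% in a 5 mm socket, 75% at 8 mm and 83% at 12 mm. The subject's starting depth then explains part of the outcome, and a model without depth leaves that part in the residual. Depth is also measured to two different landmarks according to root type, and both kinds of site enter one unstratified comparison of small arms.

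Two things are at stake: the precision of the Test-Control difference in socket fill, and how far a chance imbalance in depth moves that estimate in the sample obtained.

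**Working it through.** **Inputs from the protocol.** 20 per group, effect size 0.9, "two groups t-test with a 0.050 two-sided significance level". The 11 per arm comes from the SAP tables. **Assumptions.** The power statement is not tied to socket fill, so 0.9 is assumed for it here. Rho (within-arm correlation of CBCT-0 depth with percent fill) is not given and is varied from 0 to 0.7.

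**1. The plan's own figure.** The protocol says: "A sample size of 20 in each group will have at least 80% power to detect an effect size (ES) of 0.9". The noncentral t with 38 df and noncentrality 0.9 × √(20/2) = 2.846 gives 79.2%; the normal approximation gives 81.2%. The stated figure reproduces to within about a point. With 11 per arm (20 df) power is 52.0%.

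**2. Adding one covariate (depth).** The residual variance is multiplied by (1 − rho²) × [1 + 1/(2n − 4)]. The second term is the average cost of estimating the slope when depth is imbalanced by chance. Error df are 2n − 3.

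| rho | variance factor, n = 20 | power, n = 20 | variance factor, n = 11 | power, n = 11 |
|---|---|---|---|---|
| unadjusted | 1 | 79.2% | 1 | 52.0% |
| 0 | 1.028 | 78.0% | 1.056 | 49.6% |
| 0.3 | 0.935 | 81.7% | 0.961 | 53.4% |
| 0.4 | 0.863 | 84.7% | 0.887 | 56.7% |
| 0.5 | 0.771 | 88.4% | 0.792 | 61.5% |
| 0.7 | 0.524 | 96.9% | 0.538 | 77.9% |

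Example: at n = 20 and rho 0.5, 0.75 × (1 + 1/36) = 0.771. Break-even is near rho 0.17 with 20 per arm and 0.24 with 11.

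**3. Chance imbalance.** The difference in mean depth between arms has SD √(2/n) in baseline SD units: 0.32 at n = 20 and 0.43 at n = 11. The unadjusted fill difference moves by rho times the imbalance. For a one-SD imbalance at n = 20 that is 0 at rho 0, 0.095 outcome SD at 0.3, 0.158 at 0.5 and 0.221 at 0.7. At n = 11 it is 0, 0.128, 0.213 and 0.298.

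**4. Which rho is plausible?** Two simulated cases, with depth assumed at mean 9 mm, SD 2.5, floor 5 mm:
- Fill proportional to depth: rho about 0.
- Unfilled length unrelated to depth, mean 2 mm, SD 0.5, 1.0 or 1.5: rho about 0.70, 0.46 and 0.33.

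**5. A check within the trial's own output.** A common-slope ANCOVA on buccal plate width can be rebuilt from the SAP regression tables. Each arm's sum of squares for width is the model SS divided by slope²; for RH this is 4.9339/0.6844² = 10.53 (control) and 0.7294/0.2619² = 10.64 (test). Mean width is (intercept − mean response)/|slope|, with slopes negative: 1.72 (control) and 1.52 (test).
- **RH:** pooled slope −0.472 and within-arm |r| 0.66. The arm difference in height loss moves from −0.323 to −0.323 + 0.472 × (1.52 − 1.72) = −0.416 mm (unrounded widths). The SE falls from 0.314 to 0.244.
- **RW:** |r| 0.01. The difference goes from 0.415 to 0.413 and the SE rises from 0.344 to 0.354.

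This is a different covariate and different outcomes. The RH rebuild uses the regression table's test-arm mean of 1.027, whereas the SAP t-test table shows −1. It shows only that a baseline CBCT measure can matter a good deal, or not at all, in these data.

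**The case against.** A reader might infer that the plan certainly loses precision, or that imbalance in depth biases the result. The documents support neither. Both effects need a correlation between depth and percent fill, and if fill is proportional to depth that correlation is about zero. Under randomisation, chance imbalance is random error that the unadjusted test and its interval already allow for. It enters multiplied by rho, not in full.

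It is also tempting to count the covariate as almost free because it uses one degree of freedom. Once the slope must be estimated, the cost at rho 0 is about 1 power point with 20 per arm and about 2 with 11, so adjustment loses slightly when rho is small. The RW rebuild shows that happening with another covariate.

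Three further points stand. The protocol assigns the t-test to histomorphometry, ISQ and torque, so the effect size of 0.9 is not shown to apply to socket fill. The 11 per arm may not be the socket-fill sample, since the SAP variable labelled percent is not identified. And a single slope on depth would pool two differently defined measurements, which calls for a root-type term.

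These narrow the point. They do not remove the case for prespecifying an adjusted estimate from a value that must be measured anyway.

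**Conclusion.** The point holds as an inexpensive improvement, not as an error that invalidates the analysis. No baseline covariate is planned for an outcome built from a baseline measurement, and expressing it as a percentage replaces adjustment only under proportional fill. The gain depends wholly on an unknown rho. With 20 per arm it runs from a loss of 1.2 power points at rho 0, through gains of 2.5 at 0.3 and 9.2 at 0.5, to 17.7 at 0.7. With 11 per arm it runs from a loss of 2.3 points at rho 0 to a gain of 9.5 at 0.5. All these figures assume an effect size of 0.9 for socket fill and count depth as the only covariate.

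The weight of the point also depends on which endpoint is primary. If vital bone is confirmed, socket fill becomes a secondary outcome and this is a smaller matter.

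**What to change.** In the protocol's Statistical Analysis section and in the SAP, prespecify for socket fill a linear model with treatment, CBCT-0 socket depth (continuous) and root type (single- or multi-rooted). Report the adjusted Test-Control difference with its 95% CI, and keep the unadjusted difference as a supporting result. Write out the formula for percent fill. Because fill may be nonlinear in depth, check the linear term by plotting residuals against depth.

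The cost is a sentence or two and two error degrees of freedom; depth is already measured and root type is known. If neither covariate is related to fill, the average variance factor is about 1 + 2/(2n − 5). Power then falls from 79.2% to about 76.8% with 20 per arm (factor 1.057, 36 df), and from 52.0% to about 47.2% with 11 (factor 1.118, 18 df). Separately, state which of socket fill and vital bone is the primary endpoint.
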